Patients will return to the site for Visit 3 (Randomization) where patients who meet the criteria based on having moderate to severe symptoms based on the ANMS GCSI-DD and moderate to severe delay in gastric emptying will be randomized in a 1:1:1 ratio into three treatment groups, PCS12852 0.1 mg, PCS12852 0.5 mg or placebo.

At Visit 3, patients will answer a series of assessments including the following: Patient Assessment of Gastrointestinal Disorders Symptom Severity Index (PAGI-SYM), Patient Assessment of Upper Gastrointestinal Disorders – Quality of Life (PAGI-QOL), Patient Global Impression of Severity (PGI-S) and the Patient Global Impression of Change (PGI-C). Patients will arrive fasting and have PK samples drawn prior to receiving the first dose and at the following times after the first dose: 0.5, 1, 2, 4, 6, and 8 hours. The investigator will assess the patient through the C-SSRS as well as the Clinical Global Impression- Severity scale (CGI-S) and Clinical Global Impression – Improvement scale (CGI-I).

Patients will take their assigned treatment for 28 days. During the treatment period, the patients will also complete the ANMS GCSI-DD. Each patient will be told to take one tablet from their assigned kit at approximately the same time each morning, at least 30 minutes prior to a meal (actual dosing times will be captured via a dosing diary), starting on Day 1 for 28 days. Patients will return to the clinic on Day 7 and Day 14 to be assessed in a blinded manner for safety and tolerability of the study treatment as well as have the investigator assess the patient for suicidal tendencies or ideations via the C-SSRS.

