7.2 Loss to Follow-Up/Early Discontinuation from Study Drug

A patient will be considered lost to follow-up if they repeatedly fail to return for scheduled visits and are unable to be contacted by the study site.

The following actions must be taken if a patient fails to return to the clinic for a required study visit:

- The site must attempt to contact the patient and reschedule the missed visit as soon as possible (and within the visit window, where one is defined), counsel the patient on the importance of maintaining the assigned visit schedule, and ascertain whether the patient wishes to and/or should continue in the study.
- In cases in which the patient is deemed lost to follow-up, the Investigator or designee must make every effort to regain contact with the patient (where possible, three telephone calls and, if necessary, a certified letter to the patient's last known mailing address or local equivalent methods). These contact attempts should be documented in the patient's medical record/eCRF.
- Should the patient continue to be unreachable, he/she will be considered to have withdrawn from the study.

If a patient discontinues study drug prior to study termination, the patient will be asked to return to the clinic for an Early Termination visit. This visit will include all the study procedures of the Day 35/Visit 8 clinic visit. The Day 35 study procedures and their timing are summarized in the SoA (Table 1).

8 Study Assessments and Procedures

Study procedures and their timing are summarized in the SoA (Table 1).

Immediate safety concerns should be discussed with the Medical Monitor immediately upon occurrence or awareness to determine if the patient should continue or discontinue study treatment.

Adherence to the study design requirements, including those specified in the SoA (Table 1), is essential and required for study conduct.

All screening evaluations must be completed and reviewed to confirm that potential patients meet all eligibility criteria. The Investigator should maintain a screening log to record details of all patients screened and to confirm eligibility or record reasons for screening failure, as applicable.

Version 3.0 44 of 85 20 April 2022

Repeat or unscheduled samples may be taken for safety reasons or for technical issues with the samples.

Patient Identification Card

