8.2 Safety Assessments

Planned timepoints for all safety assessments are provided in the SoA (Table 1).

- AEs (by type, severity, and relatedness) at each visit.
- Changes in safety clinical laboratory testing and vital signs at each site visit.
- Changes in ECGs at each site visit and the potential correlation of the PK with changes in the ECG.
- Change from baseline in the C-SSRS scores over time by comparing Day 1 to Day 28.

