8.2.6 Suicidal Ideation and Behavior Risk Monitoring

Although no increased risk of suicide ideation or behavior has been documented with PCS12852, it is in a class of products that have an increased risk of suicidal ideation or behavior.

Patients being treated with PCS12852 should be monitored appropriately and observed closely for suicidal ideation and behavior (SIB) or any other unusual changes in behavior, especially at

Version 3.0 51 of 85 20 April 2022

the beginning and end of the course of study treatment. Patients who experience signs of suicidal ideation or behavior should undergo a risk assessment. All factors contributing to SIB should be evaluated and consideration should be given to discontinuation of the study treatment.

Baseline assessment of SIB will be monitored during the study using the C-SSRS by comparing Day 1 to Day 7, Day 14 and Day 28 scores. Refer to the SoA (Table 1) for timepoints.

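### The C-SSRS safety endpoint compares Day 1 with Day 28 only, which does not match Section 8.2.6 or the Schedule of Activities and misses events that resolve or lead to early stopping before Day 28

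*Combined protocol and SAP*

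**What the plan says.** The safety endpoint is worded the same way in the Synopsis, in Table 2 and in Section 8.2: "Change from baseline in the C-SSRS scores over time by comparing Day 1 to Day 28". Section 8.2.6 describes a different comparison, in which suicidal ideation and behavior are monitored "by comparing Day 1 to Day 7, Day 14 and Day 28 scores". Table 1 schedules the C-SSRS at Visit 1 (Screening), Visit 3 (Day 1), Visit 4 (Day 7), Visit 5 (Day 14), Visit 6 (Day 28) and Visit 8/ET (Day 35).

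The Day 7 and Day 14 assessments have a stated purpose: the Synopsis says patients return on those days to, among other things, "have the investigator assess the patient for suicidal tendencies or ideations via the C-SSRS". Section 8.2.6 gives the reason for the interest. It reports no documented increase in risk for the study drug itself, but says that "it is in a class of products that have an increased risk of suicidal ideation or behavior".

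Section 7 makes leaving the study automatic when treatment is permanently stopped. Section 7.2 then asks for an Early Termination visit and says of it: "This visit will include all the study procedures of the Day 35/Visit 8 clinic visit".

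**The concern.** A change score taken at one late visit is a poor detector of an event that can appear and resolve within days. It is also undefined for anyone who has left before that visit. Both problems matter more when the event itself may lead to stopping: Section 8.2.6 says discontinuing study treatment should be considered when ideation or behavior occurs. The patients most likely to have no Day 28 value therefore include the ones the endpoint exists to find.

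Three places in the protocol give one comparison and a fourth gives another, so whoever writes the tables has to guess which was meant. At stake is whether the trial's only C-SSRS endpoint gives a fair account of suicidality by arm, in a class that the protocol itself describes as carrying increased risk.

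**Working it through.** No sample size, power or error-rate figure bears on this point, so the check is a comparison of time points followed by simple counts.

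**Time points side by side** (assessments after Day 1):

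| Assessment | Scheduled in Table 1 | Compared in Section 8.2.6 | Used by the endpoint (Synopsis, Table 2, Section 8.2) |
|---|---|---|---|
| Visit 4, Day 7 | yes | yes | no |
| Visit 5, Day 14 | yes | yes | no |
| Visit 6, Day 28 | yes | yes | yes |
| Visit 8/ET, Day 35 | yes | no | no |

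The endpoint uses 1/4 = 25% of the scheduled post-baseline assessments and Section 8.2.6 uses 3/4 = 75%. Neither uses Visit 8/ET.

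**Is the two-point reading fair?** The phrase about change over time could be taken to cover the whole span from Day 1 to Day 28. Two things in the protocol point the other way. The same construction is used for the PAGI-SYM and PAGI-QOL, which Table 1 collects only on Days 1 and 28. And when Section 8.2 means every visit, it says so: a neighbouring endpoint reads "Changes in safety clinical laboratory testing and vital signs at each site visit". The two-point reading is the natural one.

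**What the endpoint returns.** Take an arm of 8, the planned size in Section 9.3, with one affected patient who had no ideation on Day 1. The cases are illustrative, not forecasts.

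- Ideation on Day 7 or 14, absent on Day 28: change = 0. Affected on the endpoint, 0/8 = 0%; affected at any post-baseline assessment, 1/8 = 12.5%.
- Ideation on Day 35 only: the same result, 0/8 against 1/8. Section 8.2.6 would also miss this case.
- Ideation that leads to stopping before Day 28: there is no Day 28 value, so the endpoint has 8 − 1 = 7 patients with data and 0/7 affected. If the Early Termination visit takes place, its C-SSRS exists but is not used. Counted at any post-baseline assessment, the figure is again 1/8 = 12.5%.

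**Does another planned summary in the protocol fill the gap?** Section 9.2.5 names adverse events, physical examination, vital signs, ECGs and laboratory values. It does not name the C-SSRS and defines no summary of treatment-emergent ideation or behavior. It does promise listings of all safety data, and it leaves the definition of safety summaries to the SAP.

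**The case against.** A reader might infer that transient ideation would go uncounted in the trial altogether, or that the report would show no emergent ideation when some had occurred. The documents do not support that.

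- Adverse events are an endpoint at each visit. Appendix 3 (Section 10.3.1) is broad enough to include new symptoms and clinically significant findings on safety assessments. Section 9.2.5 tabulates the number and percent of patients with each event, whenever it occurs. Ideation on Day 7 that was recorded as an adverse event would appear there as 1/8. This stands, with one limit: no section makes a positive C-SSRS an adverse event automatically, so it depends on the investigator.
- Care of the individual does not run through the endpoint. Section 8.2.6 says: "Patients who experience signs of suicidal ideation or behavior should undergo a risk assessment". This stands in full.
- Section 8.2.6 may describe monitoring rather than analysis, in which case the two comparisons serve different purposes and are not strictly contradictory. That is fair. But if it is monitoring only, the endpoint uses 1 of 4 assessments; if it is an analysis statement, it disagrees with the endpoint. Either way the text needs reconciling.
- A reader might also take the attention that Section 8.2.6 gives to the beginning and end of treatment as showing that leaving out Day 35 contradicts it. It does not. The last scheduled dose is on Day 28, which that section includes, and the sentence concerns close observation of patients. The omission of Visit 8/ET is shown by Table 1, not by that sentence.
- Section 9 defers detail to an SAP, and the text available contains no SAP wording on the C-SSRS. A fuller table may be planned. That limits what can be said about the final report, but it does not settle which protocol comparison was intended.
- The study is small and excludes patients with suicidal tendencies or ideation at entry, so events may be few. This bears on priority rather than on whether the endpoint is well defined.

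**Conclusion.** The point holds for the C-SSRS endpoint and no further. As written, the endpoint uses 1 of 4 scheduled post-baseline assessments, is inconsistent with Section 8.2.6 (3 of 4) and with Table 1 (all 4), returns no change for ideation or behavior that is absent on Day 28, and has no value for a patient who leaves before then. One affected patient in an arm of 8 is 12.5%, and could contribute nothing to the endpoint.

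The conclusion rests on the two-point reading of the endpoint and on there being no rule, in the text available, that carries an early termination C-SSRS into the Day 28 comparison. It does not imply that patients are left unmonitored or that the safety report as a whole would be silent. This is a minor point that is cheap to correct.

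**What to change.** Reconcile the Synopsis, Table 2, Section 8.2 and Section 8.2.6 with Table 1, so that one comparison is stated everywhere. Copying the Section 8.2.6 wording into the endpoint would not be enough, because it leaves out Visit 8/ET.

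Define the main C-SSRS summary as the number and percent of patients, by arm, with any ideation or behavior that is new or worse than the Day 1 pre-dose baseline at any post-baseline C-SSRS, including Visit 8/ET. State in the text that the Day 1 assessment is taken before the first dose, since the endpoint wording does not say so. Add the C-SSRS to the safety analyses named in Section 9.2.5 and carry the same definition into the SAP. The Day 1 to Day 28 change can stay as a supplementary summary.

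The cost is wording in a few places and one table. No visit, assessment or clinical rule changes, and all the data are already scheduled for collection.

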8.2.1 Physical Examinations

Complete physical examinations (excluding pelvic exam in women and genital exam in men, and rectal exam in both genders) are to be performed at Screening (Visit 1) and Day 28 (Visit 6). Symptom-directed (abbreviated) physical examinations may be conducted as required at Visit 3 (Day 1) Visit 4 (Day 7), Visit 5 (Day 14), and Visit 8 (Day 35).

Patients should be weighed with no shoes, in light clothing, without any outerwear. Height should be measured only at the first study visit. Any abnormality noted on the physical examination done at or following Visit 3 or the early termination visit that was not present on the physical examination at screening should be reported as an AE if considered by the Investigator to be clinically significant.

Version 3.0 49 of 85 20 April 2022

Investigators should pay special attention to clinical signs related to previous serious illnesses.

8.2.2 Vital Signs

- Heart rate (HR), respiratory rate, systolic and diastolic blood pressure (BP), weight and temperature will be assessed; the method for measuring temperature will be per the site's preference.
- BP and HR measurements will be assessed in the sitting position with a completely automated device. Manual techniques will be used only if an automated device is not available.
- BP and HR measurements should be preceded by at least 3 minutes of rest for the patient in a quiet setting without distractions (eg, television, cell phones).
- Vital signs are to be taken before blood collection for laboratory tests.

8.2.3 Electrocardiograms

A 12-lead ECG will be obtained as outlined in the SoA (Table 1) using an ECG machine after the patient has rested for 5 minutes in supine position. At Visit 3 (Randomization) and Visit 6 (Day 28), the ECG will be performed prior to the 4-hour PK draw. At Visit 4 and Visit 5, the ECG will be performed approximately 4 hours after the patient's dose. The Investigator will report whether the ECG is normal or abnormal and if the result is considered clinically significant or not.

All clinically significant ECG abnormalities occurring during the study should be documented as AEs. The ECG performed at Screening will be recorded as the baseline assessment. Standard ECG parameters, including heart rate, QRS, PR, QT, Bazett's correction for QT (QTcB), and Fridericia's correction for QT (QTcF) intervals will be measured. The ECGs will be overread by the Investigator to assess any abnormalities.

8.2.4 Clinical Safety Laboratory Tests

Refer to Appendix 2 for the list of clinical laboratory tests to be performed and the SoA (Table 1) for the timing and frequency.

The Investigator must review the laboratory report, document this review, and record any clinically significant changes occurring during the study as an AE. The laboratory reports must be filed with the source documents.

Version 3.0 50 of 85 20 April 2022

Abnormal laboratory findings associated with the underlying disease are not considered clinically significant unless judged by the Investigator to be more severe than expected for the patient's condition.

All laboratory tests with values considered clinically significantly abnormal during participation in the study or within 30 days after the last dose of study treatment should be repeated until the values return to normal or baseline or are no longer considered clinically significant by the Investigator or Medical Monitor.

- If such values do not return to normal/baseline within a period of time judged reasonable by the Investigator, the etiology should be identified, where possible, and the Sponsor notified.
- All protocol-required laboratory tests, as defined in Appendix 2, must be conducted in accordance with the laboratory manual and the SoA (Table 1).
- If laboratory values from laboratory tests not specified in the protocol and performed at the institution's local laboratory result in the need for a change in patient management or are considered clinically relevant by the Investigator (e.g., are considered to be an SAE or an AE or require dose modification), then the results must be recorded in the eCRF.

8.2.5 Pregnancy Testing

Women of childbearing potential must have a negative serum pregnancy test at the Screening Visit and a negative urine pregnancy test at baseline before dosing. A serum β -HCG test will be performed at Screening (Visit 1) and a urine pregnancy test at subsequent visits. Refer to the SoA (Table 1) for testing timepoints.

Details of all pregnancies in females and female partners of male patients will be collected after the start of study treatment and until the end of the study period (Visit 7). If a pregnancy is reported, the Investigator should inform the Sponsor within 24 hours of learning of the pregnancy and should follow the procedures outlined in Appendix 4. Abnormal pregnancy outcomes (e.g., spontaneous abortion, fetal death, stillbirth, congenital anomalies, ectopic pregnancy) are considered to be SAEs.

8.2.6 Suicidal Ideation and Behavior Risk Monitoring

Although no increased risk of suicide ideation or behavior has been documented with PCS12852, it is in a class of products that have an increased risk of suicidal ideation or behavior.

Patients being treated with PCS12852 should be monitored appropriately and observed closely for suicidal ideation and behavior (SIB) or any other unusual changes in behavior, especially at

Version 3.0 51 of 85 20 April 2022

the beginning and end of the course of study treatment. Patients who experience signs of suicidal ideation or behavior should undergo a risk assessment. All factors contributing to SIB should be evaluated and consideration should be given to discontinuation of the study treatment.

Baseline assessment of SIB will be monitored during the study using the C-SSRS by comparing Day 1 to Day 7, Day 14 and Day 28 scores. Refer to the SoA (Table 1) for timepoints.

8.3 Adverse Events, Serious Adverse Events, and Other Safety Reporting

The definitions of AEs and SAEs can be found in Appendix 3.

Adverse events will be reported by the patient or noted by the Investigator.

The Investigator and any qualified designees are responsible for detecting, documenting, and reporting events that meet the definition of an AE or SAE and remain responsible for following up AEs that are serious, considered related to the study treatment or the study, or that caused the patient to discontinue the study treatment (see Section 7).

The method of recording, evaluating, and assessing causality of AEs and SAEs and the procedures for completing and transmitting SAE reports are provided in Appendix 3.

8.3.1 Time Period and Frequency for Collecting AE and SAE Information

All AEs will be collected from the signing of the ICF. All SAEs will be collected and followed until 30 days after the final Visit (Visit 8), at the timepoints specified in the SoA (Table 1).

All SAEs will be recorded and reported to the Sponsor or designee within 24 hours of awareness, as indicated in Appendix 3. The Investigator will submit any updated SAE data to the Sponsor within 24 hours of it being available.

Investigators are not obliged to actively seek information on AEs or SAEs after the conclusion of study participation. However, if the Investigator learns of any SAE, including a death, at any time after a patient has been discharged from the study, and he/she considers the event to be reasonably related to the study treatment or study participation, the Investigator must promptly notify the Sponsor.

8.3.2 Method of Detecting AEs and SAEs

Care will be taken not to introduce bias when detecting AEs and/or SAEs. Open-ended and non-leading verbal questioning of the patient is the preferred method to inquire about AE occurrence.

Version 3.0 52 of 85 20 April 2022

8.3.3 Follow-up of AEs and SAEs

After the initial AE/SAE report, the Investigator is required to proactively follow each patient at subsequent visits/contacts. All AEs and SAEs, (as defined in Appendix 3), will be followed until resolution, stabilization, until the event is otherwise explained, or the patient is lost to follow-up (as defined in Section 7.2). Further information on follow-up procedures is given in Appendix 3.

8.3.4 Regulatory Reporting Requirements for SAE

Prompt notification within 24 hours (see Appendix 3) by the Investigator to the Sponsor of an SAE is essential so that legal obligations and ethical responsibilities towards the safety of patients and the safety of a study treatment under clinical investigation are met.

The Sponsor has a legal responsibility to notify both the local regulatory authority and other regulatory agencies about the safety of a study treatment under clinical investigation. The Sponsor will comply with country-specific regulatory requirements relating to safety reporting to the regulatory authority, Institutional Review Board (IRB)/Independent Ethics Committee (IEC), and Investigators.

Investigator safety reports must be prepared for suspected unexpected serious adverse reactions (SUSAR) according to local regulatory requirements and Sponsor policy and forwarded to investigators as necessary.

An Investigator who receives an Investigator Safety Report describing an SAE or other specific safety information (e.g., summary or listing of SAEs) from the Sponsor will review and then file it along with the Investigator's Brochure and will notify the IRB/IEC, if appropriate according to local requirements.

8.3.5 Pregnancy

Details of all pregnancies in female patients and female partners of male patients will be collected after the start of study treatment and until 7 days after the last dose.

If a pregnancy is reported, the Investigator will record pregnancy information on the appropriate form and submit it to the Sponsor within 24 hours of learning of the pregnancy and should follow the procedures outlined in Appendix 4.

Abnormal pregnancy outcomes (e.g., spontaneous abortion, fetal death, stillbirth, congenital anomalies, ectopic pregnancy) are considered to be SAEs and will be reported as such.

Version 3.0 53 of 85 20 April 2022

8.4 Pharmacokinetics

Blood samples will be collected for measurement of PCS12852 in plasma via a specific and sensitive validation bioanalytical method, at timepoints as specified in the SoA (Table 1). Clinical staff are encouraged to take the blood samples for PK analysis at the scheduled time point; however, deviations from the scheduled sample times are not considered protocol deviations. The actual date and time (24-hour clock time) of sample collections will be recorded in the source document and transcribed into the eCRF. Instructions for the collection and handling of biological samples will be provided in the Study Manual.

Samples will be used to evaluate the PK of PCS12852. Samples collected for analyses of PCS12852 plasma concentration may also be used to evaluate safety or efficacy aspects that address concerns arising during or after the study.

Genetic analyses will not be performed on these blood samples. Subject confidentiality will be maintained.

Any changes in the timing or addition of time points for any planned study assessments must be documented and approved by the relevant study team member and then archived in the Sponsor and site study files but will not constitute a protocol amendment. The IRB/IEC will be informed of any safety issues that require alteration of the safety monitoring scheme or amendment of the ICF.

Version 3.0 54 of 85 20 April 2022

9 Statistical Considerations

The statistical analysis plan (SAP) will be developed and finalized before database lock and will include a more technical and detailed description of the statistical analyses described in this section. This section is a summary of the planned statistical analyses of the most important endpoints including primary and key secondary endpoints.

